## 5.2. Endpoints

### 5.2.1. Primary Endpoint

To evaluate clinical outcomes at 12 months post procedure:

1. Improvement in MR (grade)

This will be determined by assessing the level of mitral valve regurgitation using echo, in subjects at 12 months post procedure compared to the level at baseline. The levels of regurgitation, level 0-4, will correspond to the ASE guidelines ranging from no MR, Mild MR, Moderate MR, Moderate-to-Severe MR and Severe MR, as described in Table 1 above.

2. All cause mortality

All deaths occurring from any cause post procedure.

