## 9.11. Subject Withdrawal or Discontinuation

All subjects will be encouraged to remain in the registry through the last follow-up visit at 12 months. Subjects who discontinue participation prematurely after attempted implant will be included in the analysis of results (as appropriate) but they will not be replaced in the enrollment of total study subjects. If a study subject is discontinued from the study early, the reason for discontinuation should be documented in the subject file and a Study Exit eCRF must be completed. If discontinuation is because of safety concerns, the subject shall be asked to be followed for collection of ongoing safety data outside the study. Any data collected after the exit date will not be analyzed as part of the study.

In case the subject undergoes device explant, the subject will be exited from the study.

The subjects will be exited from the study following their 12 month follow up visit. This 12 month visit will be primarily conducted via in-office visit and has a window period of additional 1 month, up to day 395 post implant. All adverse event information will be collected and reported during this follow up visit, as per timelines described above in section 11.2; subjects will be considered exited from the study on completion of their 12 month visit or when they are considered lost to follow up (after three failed attempts are made to contact the subjects).

The investigating site and Sponsor will make every effort to have all subjects complete the follow up visit schedule. A subject will not be considered lost-to-follow-up unless all efforts to obtain compliance are unsuccessful. At a minimum, the effort to obtain follow-up information must include three attempts to make contact via telephone and if contact via phone is not successful, a traceable letter from the Investigator must be sent to the subject's last known address. Should both telephone and mail efforts to contact the subject be unsuccessful, the subject's primary physician should be contacted. Subjects will then be deemed lost to follow up. All contact efforts to obtain follow-up must be documented in the subject's medical records.

If a subject discontinues the study at any time, is withdrawn from the study early, or completes all protocol required follow-up they should then be followed per the local standard of care for their condition.

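### CIP 9.11 has a lost-to-follow-up trigger that does not match its own contact sequence, no earliest day for using it, and no exception to its bar on post-exit data

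*Combined protocol and SAP*

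**What the plan says.** Three statements in CIP 9.11 matter here.

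- **Exit.** A subject leaves the study at the 12-month visit or "when they are considered lost to follow up (after three failed attempts are made to contact the subjects"). No contact method, further step or earliest day is given.
- **Lost to follow-up.** The next paragraph says: "A subject will not be considered lost-to-follow-up unless all efforts to obtain compliance are unsuccessful". It continues: "At a minimum, the effort to obtain follow-up information must include three attempts to make contact via telephone". If the calls fail, "a traceable letter from the Investigator must be sent to the subject's last known address". Then: "Should both telephone and mail efforts to contact the subject be unsuccessful, the subject's primary physician should be contacted". Only after that is the subject deemed lost.
- **Data after exit.** "Any data collected after the exit date will not be analyzed as part of the study". No exception is stated.

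Both primary endpoints are read at 12 months. CIP 5.2.1 defines mortality as "All deaths occurring from any cause post procedure". SAP 7.9.1 restricts the MR analysis to implanted subjects with a grade at both baseline and 12 months. SAP 7.4 does not impute unless otherwise specified. SAP 7.2 censors lost subjects at their last visit, correspondence, assessment or event.

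**The concern.** The short trigger omits the letter and the physician contact, which are the steps that could still establish vital status once calls fail. With 10 centres in three countries (CIP 6.1), sites may not all apply the same rule.

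Timing is the larger gap. Loss to follow-up is an alternative to the 12-month visit as a route out of the study, and nothing ties it to the close of the 12-month window. CIP 6.1 selects sites that already provide 12-month follow-up as standard care, and CIP 6.2 calls 12 months a standard timepoint at all centres. A subject who missed the middle visit may therefore still come back for a routine echo. If that subject has already been exited, the MR grade exists but falls under the post-exit bar. A death learned after exit is in the same position, although the endpoint covers deaths from any cause.

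Subjects who cannot be reached may differ from those who can. What is at stake is 12-month primary-endpoint data that could be obtained without any added procedure.

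**Working it through.** **1. The two descriptions of loss**

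| Step | Exit sentence | Next paragraph |
|---|---|---|
| Contact attempts | Three, method unstated | At least three, by telephone |
| Traceable letter | Not mentioned | Required if calls fail |
| Primary physician | Not mentioned | To be contacted if calls and letter fail |
| Earliest day | None | None |

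The two differ, and neither is said to govern or to abbreviate the other.

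**2. Timing.** The 3-6 month window closes at day 210 and the 12-month window at day 395. A subject who misses the first could be declared lost up to 395 − 210 = 185 days before the second closes. That is 365 − 210 = 155 days before the day-365 Kaplan-Meier reading in SAP 7.2.

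**3. Does the SAP repair it?** No. Censoring at last contact avoids crediting event-free time up to the exit date, but it does not lift the CIP's bar. The paired-data rule and the absence of imputation then remove the subject from the MR endpoint.

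**4. Size, for illustration.** The plan has no figure to reproduce: the 200 subjects were not statistically derived, and no loss, mortality or improvement rate is given. Assumptions: 200 implanted, 12-month mortality 5% (10 deaths), 90% of assessed survivors improved, and 10% or 20% lost.

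*Mortality.* Assume a constant hazard h = −ln(0.95)/365, common to all subjects up to day 183. Lost subjects are censored then and have hazard r × h afterwards.

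- Survival of lost subjects: S = exp[−h × 183 − r × h × 182], which gives 0.9026 for r = 3 and 0.8576 for r = 5.
- True mortality: 1 − [(1 − L) × 0.95 + L × S], where L is the fraction lost.
- Kaplan-Meier without the lost subjects' later data: 5.0%.

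| Lost | r = 1 | r = 3 | r = 5 |
|---|---|---|---|
| 10% | 5.0% | 5.5% | 5.9% |
| 20% | 5.0% | 5.9% | 6.8% |

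At 10% loss the gap is 0, 0.5 or 0.9 points. That is the gap if every lost subject could be recovered. If a random half could be, the estimate for r = 3 becomes 1 − (0.9 × 0.95 + 0.05 × 0.9026)/0.95 = 5.25%, which closes about half of it.

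*MR improvement.* There are 200 − 10 = 190 survivors. The interval is the exact 95% interval on assessed subjects. The bounds count all lost subjects as not improved, then all as improved, over 190.

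| Lost | Improved / assessed | Exact 95% interval | Bounds over 190 survivors |
|---|---|---|---|
| 0 | 171/190 | 84.8-93.9% | 90.0% |
| 20 | 153/170 | 84.5-94.1% | 153/190 to 173/190 = 80.5-91.1% |
| 40 | 135/150 | 84.0-94.3% | 135/190 to 175/190 = 71.1-92.1% |

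The planned interval hardly widens as subjects drop out, so it would not show the uncertainty that their absence creates.

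**The case against.** The best defence is that the second paragraph of CIP 9.11 is the operative rule. Its wording is mandatory, it follows directly, and it defines the status that the exit sentence relies on. The parenthetical then reads as shorthand, and a site that stopped after three calls would breach the next paragraph. This largely stands: the stricter sequence is probably what was meant. The mismatch still needs removing, because the text does not say so.

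A reader might infer that the plan permits exit at about day 210. It does not say that. The exit sentence sits in a paragraph on the 12-month visit, the section asks for every effort to complete the schedule, and CIP 9.10 treats a missed visit as a deviation rather than a reason to exit. Early exit is possible only because no limit is set.

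A reader might also infer that recoverable 12-month data are barred as a matter of course. The bar applies only to a subject declared lost, then found again, with information first collected after exit. It also follows a sentence about safety data gathered outside the study, so lost subjects may not have been its target. Its wording nevertheless covers them. The SAP's reporting of the number analysed shows how many are missing but does not bring them back.

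Finally, the registry is descriptive, with no tests or pass/fail criteria. That limits the consequences, but the 12-month estimates are its main product.

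**Conclusion.** The point holds in a limited form. CIP 9.11 contains a loss trigger that does not match its own contact sequence, sets no earliest day for using it, and bars post-exit data without an exception for subjects found again. Followed as written, these rules could discard 12-month MR grades and deaths that routine follow-up would supply.

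The documents do not allow the effect to be sized. Under the assumptions above, mortality bias is nil if loss is non-informative and about 0.5 to 0.9 points at 10% loss with a 3 to 5 times higher later hazard. It is smaller to the extent that lost subjects would never be recovered anyway. For MR the subject is lost whatever the reason.

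It would be tempting to conclude that mortality is certain to be understated, or to quote a larger contrast. For example, 6% mortality in followed subjects and 20% in a lost 10% gives 0.9 × 6% + 0.1 × 20% = 7.4%. The documents support neither step. Those rates are assumed, and the contrast supposes that every lost subject is recoverable. With a random half recovered, the figure is (0.9 × 6% + 0.05 × 20%)/0.95 = 6.7%. Subjects reachable by letter or physician should also not be counted, because the plan already requires those steps before loss is declared.

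**What to change.** Amend CIP 9.11 in three places.

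1. Delete the parenthetical in the exit sentence or point it to the next paragraph, so that calls, letter and physician contact form the only lost-to-follow-up rule.
2. State that a subject may be classed as lost only after the 12-month window closes at day 395. A missed 3-6 month visit is recorded as a deviation and the subject stays in the registry.
3. Limit the post-exit bar. MR grade and vital status obtained up to day 395 on a subject earlier thought lost are analysed, except where consent was withdrawn. Vital status should include the date last known alive as well as deaths, so that late information is not added for deaths alone.

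SAP 7.2 should confirm that the last follow-up date takes in such information.

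No visit or procedure is added. The cost is an amendment handled through the ethics committees or review boards under CIP 15.6, across 10 centres in three countries, and Study Exit forms that stay open longer.

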## 10. Risks and Benefits

### 10.1. Potential Risks

This study does not require any additional interventions other than the standard of care, therefore no risks other than the risks typically associated with a routine annuloplasty procedure and follow-ups are anticipated. All products in the study are commercially available when the study is in effect and will be used in accordance with approved labeling.

While infrequent, certain complications have been reported when using annuloplasty systems. As per the Instructions-For-Use of the product, these include the following:

- Uncorrected or recurrent regurgitation
- Stenosis
- Dehiscence
- Hemolysis (even with mild regurgitation)
- Low cardiac output
- Heart block
- Systolic anterior motion (SAM) and left ventricular outflow tract obstruction (LVOTO)
- Damage to coronary arteries
- Endocarditis
- Thrombosis
- Thromboembolism
- Anticoagulant-related bleeding or hemorrhage
- Ring fracture
- Leaflet perforation

These complications could lead to:

- Reoperation
- Explant of the annuloplasty system
- Permanent disability
- Death

There might be additional risks associated with any concomitant procedures as conducted per standard treatment of the subject which are not listed here.

In case of occurrence of adverse events, the subjects will be treated and followed up as per standard of care, as mandated by the treating physician.

## 10.2. Potential Benefits

There is no immediate benefit associated with participating in the study. However, the evidence collected in this study may help to improve future care.

## 10.3. Risk-Benefit Rationale

This study is a non-interventional study, with no additional risks to the subject relative to participation in the study, and hence, the potential benefits outweigh the risks.

## 11. Adverse Events and Device Deficiencies

### 11.1. Definitions/Classifications

**Adverse Event (AE) (ISO 14155:2011, 3.2)**

Any untoward medical occurrence, unintended disease or injury, or untoward clinical signs (including abnormal laboratory findings) in subjects, users or other persons, whether or not related to the investigational medical device.

NOTE 1 This definition includes events related to the investigational medical device or the comparator.

NOTE 2 This definition includes events related to the procedures involved.

NOTE 3 For users or other persons, this definition is restricted to events related to investigational medical devices.

**Adverse Device Effect (ADE) (ISO14155:2011 3.1)**

Adverse event related to the use of an investigational medical device.

NOTE 1 This definition includes adverse events resulting from insufficient or inadequate instructions for use, deployment, implantation, installation, or operation, or any malfunction of the investigational medical device

NOTE 2 This definition includes any event resulting from use error or from intentional misuse of the investigational medical device

## **Serious Adverse Event (SAE) (ISO 14155:2011, 3.37)**

Adverse event that

- a) led to a death
- b) led to serious deterioration in the health of the subject, that either resulted in:
  1. a life-threatening illness or injury, or
  2. a permanent impairment of a body structure or a body function, or
  3. in-patient or prolonged hospitalization, or
  4. medical or surgical intervention to prevent life-threatening illness or injury or permanent impairment to a body structure or a body function
- c) led to fetal distress, fetal death or a congenital abnormality or birth defect

*NOTE Planned hospitalization for a pre-existing condition, or a procedure required by the CIP, without serious deterioration in health, is not considered a serious adverse event.*

## **Serious Adverse Device Effect (SADE) (ISO14155:2011 3.36)**

Adverse device effect that has resulted in any of the consequences characteristic of a serious adverse event

## **Unanticipated serious adverse device effect (USADE) (ISO14155:2011 3.42)**

Serious adverse device effect which by its nature, incidence, severity or outcome had not been identified in the current version of the risk analysis report

*NOTE Anticipated serious adverse device effect (ASADE) is an effect which by its nature, incidence, severity or outcome has been identified in the risk analysis report*

## **Major adverse cardiac and cerebrovascular events (MACCE)**

- All-cause mortality
- Myocardial infarction
- Emergent cardiac surgery or re-intervention
- Stroke
- Hospitalization for Heart Failure

**Device Deficiency (DD) (ISO14155:2011 3.15)**

Inadequacy of a medical device with respect to its identity, quality, durability, reliability, safety or performance

NOTE *Device deficiencies include malfunctions, use errors and inadequate labeling*

## 11.2. Reporting of Adverse Events and Device Deficiencies

### Investigator reporting requirement

Report	Submit to	Description/Constraints
All SAE,SADE, USADE	Monitor and Sponsor	
Investigator shall report all SAEs, SADEs and USADEs to the Sponsor and monitor promptly of their occurrence. (Indian GCP section 3.3.4.3)
 
It is recommended for investigator to report all SAEs, SADEs and USADEs to the sponsor within 24 hours.
 
For reported deaths the investigator shall supply any additional information e.g. autopsy report and terminal medical reports. (Indian GCP section 3.3.4.5)

All SAE, SADE, USADE	EC	
Investigator shall report all SAEs, SADEs and USADEs to the EC promptly of their occurrence. (Indian GCP section 3.3.4.3)
 
For reported deaths the investigator shall supply any additional information e.g. autopsy report and terminal medical reports. (Indian GCP section 3.3.4.5)
 
It is recommended for investigator to report all SAEs, SADEs and USADEs to EC within 7 working days unless a stricter timeline is required by the EC.

All Device Deficiency	Monitor and Sponsor	
Investigator shall report all DDs to the Sponsor and monitor promptly of their occurrence.
 
It is recommended for investigator to report all DDs to the sponsor within 24 hours.

New information that may adversely affect safety of the subjects or the conduct of the study	EC, monitor and sponsor	Investigator shall promptly report new information that may adversely affect safety of the subject or the conduct of the study. (Indian GCP section 3.3.4.4)
--	-------------------------	--

## Sponsor reporting requirement

Report	Submit to	Description/Constraints
USADE	DCGI , Chairman of the EC	The report of the serious adverse event, after due analysis, shall be forwarded by the Sponsor to the Licensing Authority and Chairman of the Ethics Committee within 15 days the sponsor became aware of the serious adverse event. In case of the site directly reporting the USADE to EC, the Sponsor requirement to report to the EC is considered to be sufficiently met.

## Non reportable events

The events listed in the table below are expected for patients undergoing cardiac surgery, and do not need to be reported as an AE, unless they occur outside of the stated timeframe, are otherwise considered to be an AE according to the investigator, or are suspected or confirmed to be device-related.

Body Category	Occurrence	Timeframe (hours) post procedure
Hematologic	Blood transfusion and anemia occurring during the procedure within expected ranges (part of the regular hospital protocol)	0
Hematologic	Any bleeding during the procedure	0
Hematologic	Any bleeding after procedure with < 3 units blood transfusion, or < 1 liter blood loss	24
Cardiac	Short transient episode of arrhythmia (including ventricular fibrillation) during procedure	0
Central Nervous System	Confusion, anxiety and/or disorientation (other than TIA/stroke) starting within 48 hours with or without medical intervention	120 (5 days)
Central Nervous	Temporary change in mental status (other than	72

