## 9.8. Assessment of Safety

Serious Adverse Events and Device Deficiencies throughout the study will be collected and recorded in the AE and DD CRF's. All Adverse Events and Device Deficiencies will be reviewed by Medtronic Safety Representative. Safety Representative will ensure the timely review and reporting of all events. Safety assessment will be documented in the safety database. The types of events and reporting requirements are described in section 11 below.

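### CIP section 11.2 contradicts itself on early bleeding: every SAE must be reported, yet the non-reportable list covers bleeds within 24 hours with no exception for serious ones

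*Combined protocol and SAP*

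**What the plan says.** - **The duty.** The investigator reporting table in CIP section 11.2 states: "Investigator shall report all SAEs, SADEs and USADEs to the Sponsor and monitor promptly of their occurrence". It makes no exception for particular kinds of event.
- **The exemption.** Later in the same section, under Non reportable events, events expected after cardiac surgery "do not need to be reported as an AE, unless they occur outside of the stated timeframe". Two further exceptions follow: the exemption also lapses for events that "are otherwise considered to be an AE according to the investigator, or are suspected or confirmed to be device-related".
- **The bleeding row.** The list includes "Any bleeding after procedure with < 3 units blood transfusion, or < 1 liter blood loss", with a timeframe of 24 hours.
- **The SAE definition.** CIP section 11.1 defines an SAE as an adverse event with one of several outcomes. One is "medical or surgical intervention to prevent life-threatening illness or injury or permanent impairment to a body structure or a body function"; a lengthened hospital stay is another.
- **What is collected.** CIP section 9.8 says "Serious Adverse Events and Device Deficiencies throughout the study will be collected and recorded in the AE and DD CRF's". Sections 9.9.2 and 9.9.3 ask for SAEs, including MACCE, at implant and at discharge, each with an adverse event form.
- **What is analysed.** SAP section 7.10 plans a listing of adverse events for attempted-implant subjects and proportions by MedDRA class and term.

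**The concern.** Two rules in one section give different answers for the same event. An early bleed that needs intervention to avert a life-threatening state is an SAE under section 11.1 and so falls under the duty to report. It can also sit on the list of events that need not be reported. The list has no exception for seriousness, and the bleeding row bounds severity only through its two limits, joined in a way that lets either one be exceeded.

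At stake is whether the early bleeding shown in the SAP section 7.10 outputs is complete. CIP section 6.1 plans 10 centers, and section 12 provides neither a data monitoring committee nor a clinical events committee that might even out differences in how centers read the rule.

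**Working it through.** There is no plan figure to reproduce, so the check is a reading of the text.

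**Step 1: what the connector exempts.** Inputs are the two limits in the bleeding row, for bleeding within 24 hours.

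| Transfused | Blood lost | Exempt with *or* | Exempt with *and* |
|---|---|---|---|
| under 3 units | under 1 liter | yes | yes |
| under 3 units | 1 liter or more | yes | no |
| 3 units or more | under 1 liter | yes | no |
| 3 units or more | 1 liter or more | no | no |

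Read literally, 3 of 4 combinations are exempt, including both in which one limit is exceeded. With *and*, it is 1 of 4. These are counts of combinations, not of patients. The table does not settle the intended sense: in the low-grade fever row, *or* merely joins one threshold expressed in two units.

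**Step 2: whether another clause removes serious bleeds from the list.** The lead sentence has three exceptions: outside the timeframe, considered an AE by the investigator, or device-related. Seriousness is not one of them. Several other rows carry their own severity bound, such as excluding stroke, limiting dyspnea to mild, or limiting effusion to cases that need no puncture. The post-procedure bleeding row has only its two limits.

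**Step 3: which rule wins.** The duty covers all SAEs. The exemption covers AEs, and section 11.1 makes every SAE an AE. So the exemption can be read as reaching serious events, or the duty can be read as overriding it. No sentence ranks them.

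**Step 4: which events can be lost.** Collection up to the 3-6 month visit is of SAEs, so there are three cases for a bleed within 24 hours:

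- Not serious: not collected, whichever connector is used.
- Serious, and the site follows the all-SAE duty: reported, whichever connector is used.
- Serious, and the site follows the list: may be omitted in 3 of the 4 combinations with *or*, in 1 of 4 with *and*, and in none if serious events are carved out.

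Only the third case is affected. It shrinks further where the investigator considers the bleed an AE or suspects the device.

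**Step 5: where the loss would show.** Bleeding is not a primary or secondary endpoint and is not a named MACCE component. It could reach MACCE only through another component, such as urgent cardiac surgery. The affected outputs are the adverse event listing and the MedDRA summary.

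**The case against.** The strongest reply is that the plan already secures serious bleeds. Section 11.2 requires all SAEs, section 9.8 requires them throughout the study, and the discharge visit in section 9.9.3 asks for every SAE since implant, which covers the 24-hour window. Table 4 also records re-operation at discharge. The exemption is permissive, lasts 24 hours, and yields to investigator judgement and to suspected device-relatedness. The row might also mean two alternative measures, whichever the site happens to record.

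Much of this stands. A reader might infer that a bleed exceeding one limit is non-reportable outright and drops out of the safety data; the documents do not support that, because the separate duty to report SAEs remains in force. A reader might also attach a number by applying an assumed bleeding rate to the 200 subjects. That would count the wrong thing: non-serious bleeds are not collected under either connector, and serious ones are due under the general duty under both. Nor does the point undermine a comparison of centers, since SAP section 7.3 plans no center analysis.

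The reply does not remove the conflict. Citing the all-SAE duty assumes that it prevails, which is exactly what the section leaves unsaid. Relying on investigator judgement leaves the answer to each site.

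**Conclusion.** The point holds as an internal conflict in CIP section 11.2, together with a connector that does not bound the bleeding exemption. A serious bleed in the first 24 hours can be treated as non-reportable at some sites and may be missing from the SAP section 7.10 outputs. Any error is towards under-counting. Its size cannot be estimated: the documents give neither a bleeding rate, nor the share of such bleeds that would be serious, nor how sites read the rule.

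The conclusion assumes that at least some sites would let the list override the general duty, which the text permits but does not require. Severity is minor: no endpoint is a bleeding endpoint, and the study has no hypothesis tests or pass/fail criteria.

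**What to change.** 1. Add to the lead sentence of the Non reportable events table that no exemption applies to an event meeting the SAE definition in section 11.1, so that the all-SAE duty prevails. This is the main repair and it serves every row.
2. Reconcile the connector in the bleeding row so that exceeding either existing limit removes the exemption: *and* in place of *or*, if that is the sponsor's intent. Both limits stay as they are. Once the first change is made, this one alters little in the data collected, but it removes a misreading.

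The cost is one clause and one word, but in a CIP amendment. Section 15.6 sends significant amendments to each site's EC/IRB for approval, and minor ones for notification or approval where applicable, across the 10 planned centers. A few more SAE reports may follow. No clinical management changes.
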